4.1.2. Inclusion Criteria

Subjects will be eligible to participate if the following criteria are met:

- Ability to provide written informed consent and comply with study assessments for the full duration of the study
- Age \geq 18 years
- Active radiation retinopathy resulting from any form of radiation treatment. Radiation retinopathy is defined as any of the following: retinal hemorrhages, exudates, edema, and/or neovascularization, not attributable to other causes.
- Best Corrected Visual Acuity (BCVA) of 20/25-20/400 in the study eye

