Appendix E

Study Drug Retreatment Criteria and Associated Images

Clinical evidence of recurrent active radiation retinopathy necessitating treatment with intravitreal injection of ranibizumab 0.5 mg includes any of the following:

1. Evidence of true subretinal or intraretinal fluid in the study eye on SD-OCT.
2. Increase in central subfield thickness on SD-OCT of 50 microns or more due to active radiation retinopathy.
3. ETDRS vision loss of 5 letters or more from the previous measurement with corresponding SD-OCT evidence of active disease activity in the macula.

A "dry" macula with no clinical evidence of active radiation retinopathy that does not necessitate treatment with intravitreal injection of ranibizumab 0.5 mg is defined by the following:

[figure not shown]
1. Resolution of active radiation retinopathy on both clinical and SD-OCT evaluation with resolution of intraretinal or subretinal fluid in the study eye.
2. Hypo-dense areas not consistent with true subretinal or intraretinal fluid or active disease activity do not necessitate treatment.
3. Small chronic intraretinal cystic areas observed on SD-OCT associated with outer-retinal atrophy believed to not be affecting visual acuity in the study eye do not necessitate treatment. These cysts, when present while considering the macula dry, should be marked in the SD-OCT interpretation area on the chart note.
4. Minimal increased retinal thickening in the study eye on SD-OCT without definitive intraretinal or subretinal exudative fluid does not necessitate treatment.

[figure not shown]
[figure not shown]
Associated Images

SD-OCT Findings Consistent with Active Radiation Retinopathy or Exudative Disease Activity
Necessitating Treatment with Intravitreal Injection

SD-OCT Findings Consistent with Inactive Radiation Retinopathy Not Requiring Treatment with
Intravitreal Injection

ppendix F

Grading Scale for Intraretinal Hemorrhages, Hard Exudates, and Neovascularization

The severity of intraretinal hemorrhages, hard exudates, and neovascularization in the study eye should be assessed through slit lamp and/or indirect examination by the PI or Sub-Investigator. The PI or Sub-Investigator should grade the severity of intraretinal hemorrhages, hard exudates, and neovascularization based on the grading scale below.

Intraretinal Hemorrhages

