The grading scale below is measured by individual hemorrhage. This grading scale should be used to measure the severity of intraretinal hemorrhages in the study eye.

Grading Scale	Interpretation
0	None
1	0 - 5
2	5 - 10
3	10 - 20
4	➤ 20

ard Exudates

The grading scale below should be used to measure the severity of hard exudates in the study eye.

Grading Scale	Interpretation
0	None
1	Presence of non-visualy significant hard exudate(s)
2	Presence of macular visually significant hard exudate(s)

Neovascularization

The grading scale below should be used to measure the severity of neovascularization in the study eye.

Grading Scale	Interpretation

0	None
1	Early neovascularization including IRMA or non-clinically apparent neovascularization detectable on FA but minimally detectable on exam
2	Clinically apparent neovascularization including NVI, NVD, and/or NVE
3	Neovascular glaucoma with documented elevated IOP requiring IOP therapy

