6. ANALYSES

All outcomes will be presented using descriptive statistics. For comparison of groups for primary and secondary outcomes, variables of interest will be statistically analyzed using analysis of variance (ANOVA), Student's t-tests, Chi square and Fisher's exact test. ETDRS data will be obtained for all visits

for all 40 of the participants. Bonferroni correction was applied to all pairwise comparison analyses for this study.

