6.2 Secondary Outcomes

The secondary analysis will compare cohorts (A vs. B vs. C) on their mean CMT measurements at baseline, week 48 and week 104. The secondary analysis will also compare percentage of eyes with intraretinal exudates, retinal hemorrhage, and neovascularization at baseline, week 48 and week 104. The frequency of injection will be compared between cohorts and the correlation between injection frequency and CMT and/or ETDRS BCVA will be assessed.

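### SAP 6.2 compares graded hemorrhage, exudate and neovascularization only as percentages of eyes with the sign, so changes among the non-zero grades do not count; separately, the Appendix F hemorrhage bands overlap (minor)

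*SAP*

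**What the plan says.** Appendix F of the protocol asks for severity, not mere presence: "The PI or Sub-Investigator should grade the severity of intraretinal hemorrhages, hard exudates, and neovascularization based on the grading scale below". It sets out three scales:

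- Intraretinal hemorrhage, grades 0–4. On the unit it says "The grading scale below is measured by individual hemorrhage". The bands are none, 0–5, 5–10, 10–20 and more than 20.
- Hard exudate, grades 0–2: none, not visually significant, and macular and visually significant.
- Neovascularization, grades 0–3, the top grade being "Neovascular glaucoma with documented elevated IOP requiring IOP therapy".

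SAP 6.2 turns all three into proportions: "The secondary analysis will also compare percentage of eyes with intraretinal exudates, retinal hemorrhage, and neovascularization at baseline, week 48 and week 104". It does not refer to Appendix F or say which grade counts as having the sign. Its terms also differ slightly: intraretinal exudates where Appendix F has hard exudates, and retinal hemorrhage where Appendix F has intraretinal hemorrhages.

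SAP section 6 names the methods: "variables of interest will be statistically analyzed using analysis of variance (ANOVA), Student's t-tests, Chi square and Fisher's exact test". No rank or ordinal method is among them. The same section promises descriptive statistics for all outcomes and a Bonferroni correction for all pairwise comparisons.

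**The concern.** There are two separate defects.

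**The comparison discards severity.** Once an eye has a sign, no change among the non-zero grades counts. An eye improving from more than 20 hemorrhages to 3 and one worsening from 3 to more than 20 both stay in the same category. These signs belong to the entry definition ("Radiation retinopathy is defined as any of the following: retinal hemorrhages, exudates, edema, and/or neovascularization"), so at least some eyes will start above grade 0. If nearly all do, a present/absent comparison has little room to show a difference between cohorts.

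**The hemorrhage bands are not exclusive.** A grader who follows the table literally can record either of two grades at certain counts. With grading by the investigator or sub-investigator at four sites, the grade at a band edge may depend on the grader.

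At stake is how well a lower-tier comparison of retinopathy severity uses data that the protocol already requires. The visual acuity analysis is not affected.

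**Working it through.** **1. The plan's own figure.** There is none for these signs. The one calculation in the SAP (section 2.1: n=41, 80% power, one-way ANOVA, 0.05) gives no effect size and is not tied to this analysis.

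**2. Band overlap.** Checking whole-number counts against the five bands:

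| Count | Grades that fit |
|---|---|
| 0 | 0 and 1 |
| 5 | 1 and 2 |
| 10 | 2 and 3 |
| 20 | 3 only |

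Every other count fits one grade. If an eye has the sign at grade 1 or above (an assumption, since the SAP does not say), moving between grades 1 and 2 or between 2 and 3 leaves the percentage unchanged. Only the overlap at 0 can change it. All three overlaps would affect an analysis of the grade.

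**3. Information kept by present/absent.** Under proportional odds, the efficiency of the binary split relative to the full grade is

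3·p0·(1 − p0) / (1 − Σ pᵢ³),

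where p0 is the share of eyes at grade 0 and pᵢ the share at each grade. The documents give no grade distribution, so assume the non-zero grades are equally likely.

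- Hemorrhage, p0 = 0.05: each other grade has 0.95/4 = 0.2375. Numerator 3 × 0.05 × 0.95 = 0.1425. Denominator 1 − (0.05³ + 4 × 0.2375³) = 0.946. Ratio 0.15.
- Hemorrhage, p0 = 0.50: each other grade has 0.125. Numerator 0.75. Denominator 1 − (0.125 + 4 × 0.125³) = 0.867. Ratio 0.87.

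| p0 | Hemorrhage (5 levels) | Neovascularization (4) | Exudate (3) |
|---|---|---|---|
| 0.05 | 15% | 16% | 18% |
| 0.10 | 28% | 29% | 33% |
| 0.20 | 50% | 51% | 56% |
| 0.30 | 66% | 67% | 71% |
| 0.50 | 87% | 87% | 89% |
| 0.80 | 99% | 99% | 99% |

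More than half is lost only when p0 is below about 0.20 (hemorrhage), 0.19 (neovascularization) or 0.17 (exudate).

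**4. Power for the hemorrhage grade.** Assumed control grades at week 48, in percent for grades 0 to 4: 5/30/25/20/20, 15/30/25/15/15, 30/30/20/10/10 and 50/20/15/10/5. The other cohort follows from a common cumulative odds ratio of 4. For example, 30% at none has odds 0.30/0.70 = 0.429; times 4 is 1.714, or 1.714/2.714 = 63% at none. Two-sided 0.05, 16 versus 16, at least 2,000 simulated trials per setting (standard error about 1 point at 50%):

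| Control eyes at none | Wilcoxon on grade | Fisher, present/absent | Chi-square, present/absent |
|---|---|---|---|
| 5% | 54% | 6% | 14% |
| 15% | 54% | 24% | 41% |
| 30% | 52% | 33% | 49% |
| 50% | 44% | 29% | 45% |

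With 8 versus 16, Wilcoxon against chi-square is about 38% against 3%, 39% against 26%, 38% against 38%, and 32% against 36%.

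**5. At the corrected level.** Three cohort pairs give 0.05/3 = 0.0167. With 16 versus 16, Wilcoxon falls to about 27–35% over the four scenarios. For the first three, Fisher has about 1%, 12% and 21%, and chi-square 7%, 23% and 33%.

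**The case against.** The strongest reply is that the size of the loss is unknown and may be small. Any one of four findings suffices for entry, so an eye may enter with edema alone and be at grade 0 for everything graded here. Treatment up to week 48 could make grade 0 commoner still. With half the eyes at none, chi-square, which the SAP lists, does as well as the rank test. This stands. A reader might infer from the collapsed scales that most of the collected information is lost; the documents do not support that, because it requires fewer than about one eye in five at none and they give no distribution.

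A reader might also infer that the overlapping bands cause the loss. They do not. The overlaps at 5 and 10 cannot move a present/absent percentage, and at 0 the label for grade 0 gives a grader who sees no hemorrhage an obvious choice.

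Third, a rank test does not rescue the comparison. At the Bonferroni level its power stays near one third even for an odds ratio of 4, and at an odds ratio of 2 it has 13–18% at 0.05. That also stands: the main limit is 40 patients.

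Finally, a percentage of eyes with a sign is a readable summary, and the promise of descriptive statistics does not rule out grade tables. True, but neither does it commit to them, and the only comparison named is of percentages.

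**Conclusion.** Upheld as a minor point. Two things are certain from the text: the named comparison of three graded signs is binary with no stated threshold, and the hemorrhage bands overlap at 0, 5 and 10.

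The cost of the binary comparison can only be given as a range. Under the stated assumptions the rank test gains roughly 40 points over chi-square when 5% of control eyes are at none (54% against 14%), about 3 points at 30% (52% against 49%), and nothing at 50% (44% against 45%). It exceeds Fisher in every 16-versus-16 scenario tabulated. These figures rest on assumed grade distributions, a common odds ratio of 4, nominal cohort sizes and complete data.

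The rating is minor because none of the three signs, as graded, is listed as a secondary outcome in SAP 4.2 or protocol 3.3.2. Neovascular glaucoma is listed there, so the top neovascularization grade is partly covered already. No primary conclusion depends on this.

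**What to change.** 1. In Appendix F, make the hemorrhage bands 0, 1–5, 6–10, 11–20 and more than 20. Check once any grade already recorded at a band edge.
2. In SAP 6.2, use the Appendix F terms and define an eye with the sign as grade 1 or above.
3. Compare the ordinal grade, or its change from Day 0, for all three signs at weeks 48 and 104: Kruskal-Wallis across cohorts, then Wilcoxon tests for the pairs under the Bonferroni correction already planned. Choose between grade and change before the data are examined.
4. Keep the percentages, and add a Day 0 to follow-up grade-shift table by cohort, both as description.

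Do not stratify over all five Day 0 grades or rely on a proportional-odds model alone; 40 eyes in three cohorts are too sparse for either.

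The cost is a table correction, a few sentences in the SAP, the band-edge check and a little extra analysis. No new data are needed. If most eyes prove to be at none, the rank test may lose a little against chi-square: about 1 point at 16 versus 16 and about 4 points at 8 versus 16 in the 50% scenario.

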- Cohort B (n=16) will receive monthly treatment of 0.5 mg ranibizumab for 48 weeks. 1 week (\pm 3 days) after the initial dose of ranibizumab is delivered, the subject will have peripheral targeted-retinal photocoagulation (TRP) to areas of peripheral retinal ischemia based on wide field angiography that was performed at the screen visit. After the first session of TRP, subjects will have a repeat wide field angiogram at

week 24 and week 36 and will receive additional TRP as needed (PRN) to areas of peripheral retinal ischemia.

- Cohort C (n=16) will receive a loading dose (3 consecutive monthly doses) of 0.5 mg ranibizumab followed by PRN treatment with 0.5 mg ranibizumab. 1 week (\pm 3 days) after the initial dose of ranibizumab is delivered, the subject will have peripheral targeted-retinal photocoagulation (TRP) to areas of peripheral retinal ischemia based on wide field angiography that was performed at the screen visit. After the first session of TRP, subjects will have a repeat wide field angiogram at week 24 and week 36 and will receive additional TRP as needed (PRN) to areas of peripheral retinal ischemia.

For subjects in Cohort C, PRN treatment of ranibizumab 0.5 mg, starting at week 12 is defined by the Study Drug Retreatment Criteria and Associated Images in Appendix E.

For subjects in Cohort B or Cohort C, PRN treatment of TRP at week 24 and week 36 is defined in Appendix C under TRP Administration and PRN Retreatment Criteria.

Week 52 through Week 101:

All cohorts will enter a treat and extend protocol for IVT ranibizumab retreatment beginning at week 52. At any visit where a dry macula is achieved in the study eye, the visit interval between IVT ranibizumab treatments will be lengthened by 1 week. A dry macula is defined as the resolution of recurrent or persistent fluid based on SD-OCT, slit lamp examination, and/or indirect ophthalmoscopy.

After a subject has been extended beyond a monthly visit interval between IVT ranibizumab treatments, the visit interval will be reduced by 1 week, if the study eye develops recurrent disease activity. Recurrent disease activity is defined as recurrent or persistent fluid based on SD-OCT, slit lamp examination, and/or indirect ophthalmoscopy.

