4.3.2. Dosage, Administration, and Storage of Ranibizumab

4.3.2.1. Dosage

Subjects will receive intravitreal injections of 0.5 mg ranibizumab according to their specific cohort treatment schedule.

Ranibizumab retreatment criteria for Cohort C, will be based on:

- On SD-OCT, recurrent or persistent fluid
- Treating physician discretion based on clinical evaluation/finding

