2. OVERVIEW OF STUDY DESIGN

This trial will compare the results of 3 different combinations of therapy to assess the efficacy of peripheral targeted retinal photocoagulation (TRP) applied to areas of retinal nonperfusion and poor perfusion combined with ranibizumab injections for the treatment of macular edema secondary to radiation retinopathy. Specifically, this trial will evaluate the ability to reduce the monthly treatment burden by eliminating areas of peripheral ischemia as detected by wide field fluorescein angiography. This peripheral ischemic retina is likely a major VEGF production site. By selectively eliminating these ischemic areas with angiography-guided laser ablation while preserving more perfused areas of peripheral retinal, pathological levels of VEGF may be significantly reduced, translating into fewer necessary monthly intravitreal injections while preserving useful peripheral visual field. The study will include 3 cohorts followed for a total of 104 weeks.

Subjects will be randomized into one of three treatment cohorts in a 1:2:2 ratio.

Day 1 through Week 48:

- Cohort A (n=8) will receive monthly treatment of 0.5 mg ranibizumab for 48 weeks. Monthly treatment is defined as every 28 days (+/- 7 days).
- Cohort B (n=16) will receive monthly treatment of 0.5mg ranibizumab for 48 weeks. 1 week (+/-3 days) after the initial dose of ranibizumab is delivered, the subject will have peripheral targeted-retinal photocoagulation (TRP) to areas of peripheral retinal ischemia based on wide field angiography that was performed at the screen visit. After the first session of TRP, subjects will have a repeat wide field angiogram at week 24 and week 36 and will receive additional TRP as needed (PRN) to areas of peripheral retinal ischemia.
- Cohort C (n=16) will receive a loading dose (3 consecutive monthly doses) of 0.5mg ranibizumab followed by PRN treatment with 0.5mg ranibizumab. 1 week (+/- 3 days) after the initial dose of ranibizumab is delivered, the subject will have peripheral TRP to areas of peripheral retinal ischemia based on wide field angiography that was performed at the screen visit. After the first session of TRP, subjects will have a repeat wide field angiogram at week 24 and week 36 and will receive additional TRP as needed to areas of peripheral retinal ischemia.

See RRR protocol for TRP and PRN treatment criteria.

Week 52 through Week 101:

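### The injection-frequency correlation in SAP 6.2 cannot show an effect of injections, because the OCT findings help to set the frequency

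*SAP*

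**What the plan says.** SAP 6.2 lists the secondary analyses. After the comparison of injection frequency between cohorts it adds that "the correlation between injection frequency and CMT and/or ETDRS BCVA will be assessed". It does not say which cohorts enter, which period is counted, whether thickness and acuity are levels or changes, which coefficient is used, or what the result is for. SAP 6 names tests for comparing groups but no correlation method.

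How the frequency arises is set out elsewhere:

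- **Cohorts A and B to week 48.** SAP 2: "Cohort A (n=8) will receive monthly treatment of 0.5 mg ranibizumab for 48 weeks". Protocol 3.2: "Cohort B (n=16) will receive monthly treatment of 0.5 mg ranibizumab for 48 weeks".
- **Cohort C to week 48.** Three loading doses, then as-needed treatment. Protocol 3.2: "For subjects in Cohort C, PRN treatment of ranibizumab 0.5 mg, starting at week 12 is defined by the Study Drug Retreatment Criteria". Appendix E lists three criteria, any one of which is enough: "Evidence of true subretinal or intraretinal fluid in the study eye on SD-OCT"; "Increase in central subfield thickness on SD-OCT of 50 microns or more due to active radiation retinopathy"; and "ETDRS vision loss of 5 letters or more from the previous measurement with corresponding SD-OCT evidence of active disease activity in the macula". Protocol 4.3.2.1 adds "Treating physician discretion based on clinical evaluation/finding".
- **All cohorts, weeks 52 to 101.** Under Protocol 3.2 and SAP 2, the interval grows by one week when the macula is dry. Once it exceeds a month, it shrinks by one week when there is fluid. The maximum is 12 weeks.

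**The concern.** A correlation between how often an eye was injected and how thick the retina is, or how well the eye sees, would normally be read as information about dose and response. Here the count is partly a record of earlier OCT findings. Eyes that stay wet are injected more often, and they also tend to be thicker at the end. That is treatment by indication, and it produces a positive association with thickness whether or not the injections work. If they do work, the benefit pulls the other way, and the correlation cannot separate the two.

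Pooling adds a second problem. Cohorts A and B share one protocol-set count to week 48 and Cohort C has its own range, so part of any pooled correlation is a difference between regimens rather than between eyes.

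The stakes are limited but real. Lowering the injection burden is a stated purpose of the trial (Protocol 3.2, SAP 2), so readers will look at any reported link between frequency and outcome.

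**Working it through.** The documents give no figure for this correlation, so there is none to reproduce. I take CMT, which the SAP does not define, to be an SD-OCT macular thickness measure.

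**Step 1: how far the count can vary.** This assumes every dose is given, four-weekly visits that include weeks 12 and 48, and an interval that starts at 4 weeks at week 52 and does not fall below 4.

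- A and B to week 48: 48/4 + 1 = 13 doses, with no planned variation. No correlation can be computed within these cohorts over this period.
- C to week 48: 3 loading doses plus up to (48 − 12)/4 + 1 = 10 as-needed doses, so 3 to 13.
- Weeks 52 to 101, any cohort: always wet gives (100 − 52)/4 + 1 = 13 doses. Always dry gives doses at weeks 52, 57, 63, 70, 78, 87 and 97, which is 7.
- Whole study: A and B from 13 + 7 = 20 to 13 + 13 = 26; C from 3 + 7 = 10 to 26.

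All planned variation within a cohort therefore comes from the retreatment and interval rules.

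**Step 2: simple zero-effect model.** Sixteen eyes have thickness at 10 as-needed visits with a constant within-eye correlation. An injection is given when thickness is above average and has no effect. The injection rule and the correlation are assumptions; neither is in the documents. Mean Pearson r between injection count and final thickness level in Cohort C, with the final visit left out of the count:

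| Within-eye correlation | Mean r |
|---|---|
| 0.2 | 0.33 |
| 0.3 | 0.44 |
| 0.6 | 0.69 |
| 0.8 | 0.80 |

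At 0.6, 92% of simulated cohorts reach two-sided p<0.05. Counting the final visit raises r (0.47 at 0.2; 0.75 at 0.6). Pooling all 40 eyes gives r of about 0.11 to 0.36. For change in thickness from baseline in Cohort C, mean r is 0.03 to 0.10, with p<0.05 in 4% to 6% of cohorts, which is the nominal rate.

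**Step 3: model closer to the protocol's rules.** Cohorts of 8, 16 and 16; 1,000 trials per scenario; zero injection effect; both phases simulated. All values are assumed: mean thickness 380 microns, within-eye SD 60 with weekly autocorrelation 0.9, fluid when thickness exceeds 320, acuity SD 15 letters, and between-eye SD 40, 80 or 120. The between-eye share of variance is then 1600/5200 = 0.31, 6400/10000 = 0.64 or 14400/18000 = 0.80. The triggers in C are fluid, a 50-micron rise, or a 5-letter loss with fluid. Physician discretion is not modelled.

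| Count against thickness level | Mean r | Trials with p<0.05 |
|---|---|---|
| C, week 48 | 0.57 to 0.80 | 70% to 99% |
| All cohorts, week 48 | 0.30 to 0.42 | 50% to 82% |
| A and B, week 104 | 0.40 to 0.73 | 51% to 100% |
| All cohorts, week 104 | 0.36 to 0.65 | 66% to 100% |

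For acuity level the result depends on the assumed thickness–acuity correlation:

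- At −0.4, r is −0.12 to −0.30 and p<0.05 occurs in 11% to 37% of trials.
- At −0.2 (between-eye SD 80 only), p<0.05 occurs in 6% to 9%.
- At 0 (same SD), 4% to 5%.

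For change from Day 0 in Cohort C at week 48, r is 0.09 to 0.14 for thickness (4% to 7%) and 0.00 to −0.10 for acuity (4% to 6%). Change was not checked for the pooled cohorts or at week 104.

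**The case against.** The strongest case against has four parts.

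- **The SAP makes no causal claim.** It says only that the correlation will be assessed, and SAP 6 promises descriptive statistics for all outcomes. The same sentence of SAP 6.2 already plans the comparison of frequency between randomised cohorts. This stands: a reader might infer that the plan intends a dose-response analysis, but no wording supports that. What remains is that nothing labels the correlation as descriptive, and it sits within the secondary analysis.
- **The bias is not general.** A reader might infer that a false association appears for every version of the outcome. It does not: it is near nominal for change from Day 0 in Cohort C, and modest or absent for acuity level unless thickness and acuity are clearly linked. The SAP does not say whether level or change is meant. Its thickness comparison in 6.2 refers to measurements at each time point, which suggests levels; its primary acuity outcome is a change.
- **The rules are easily overstated.** A reader might infer that frequency is fixed in A and B throughout, or that letter loss alone is an Appendix E trigger. The first holds only to week 48. The second is wrong, because Appendix E requires accompanying OCT activity. The first correction widens the problem to all cohorts; the second weakens the acuity part.
- **The sizes rest on assumptions.** No variance, within-eye correlation or fluid threshold is in the documents, and Appendix E exempts some chronic cysts and minimal thickening from treatment. This stands, so ranges are given. The direction for thickness level follows from the rules themselves.

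**Conclusion.** The point holds in a limited form. As planned, the correlation cannot show an effect of injections, because the findings that drive dosing are closely tied to the outcome. In Cohort C to week 48, with no treatment effect, the expected correlation with thickness level is about 0.3 to 0.8 for a within-eye correlation of 0.2 to 0.8. It is smaller when cohorts are pooled. By week 104 the same mechanism operates in A and B. The acuity part is weaker and conditional, and for change from Day 0 the bias is close to nil under these assumptions.

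The conclusion does not touch the primary analysis or the randomised comparison of injection frequency. It concerns one clause of the secondary analysis and is a cheap improvement, not a flaw that threatens the trial.

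**What to change.** In SAP 6.2, do one of two things.

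1. Drop the correlation.
2. Keep it, labelled as a description of how often the retreatment and interval rules were met. State whether thickness and acuity are levels or changes. Show it by cohort and by period (to week 48; weeks 52 to 101), without p-values and without pooling cohorts. For A and B to week 48, report only the doses given and missed.

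In either case, add a sentence that inference on injection regimen and vision or thickness comes only from the randomised comparison of A, B and C.

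The cost is one or two sentences of SAP text. No data collection, visit or treatment rule changes. The downside is that one secondary analysis loses its inferential standing.
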